5.2. Safety Review Committee

An SRC will perform ongoing reviews of safety, tolerability, and available study data collected throughout the study with the primary purpose of protecting the safety of subjects participating in this clinical study. The SRC will be governed by an SRC Charter that will be finalized prior to screening the first subject.

The SRC will undertake safety data review prior to initiation of dosing a new cohort in the study in accordance with the SRC Charter. In addition, ad hoc SRC meetings may take place as needed, eg, for a significant safety event such as a cohort stopping criterion being reached ([Section 5.6](#)).

While decisions to suspend dosing will be made according to predetermined stopping rules ([Section 5.6](#)), the SRC may also recommend discontinuation of the study to the Sponsor. The SRC membership composition and data review requirements are described in detail in the SRC Charter.

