5.6.1. Cohort Stopping Rules

If any of the criteria described below are met, as determined by the Sponsor, cohort dosing will be suspended or stopped:

- Any safety finding assessed as related to study drug that, in the opinion of the sponsor or the investigator, warrants suspension of further dosing of subjects until more fully assessed
- If a sentinel subject experiences a study drug-related Grade 3 or higher AE
- If 2 or more subjects experience the same study drug-related Grade 3 or higher AE
- If 1 or more subjects experience a study drug-related serious adverse event (SAE)
- If 1 or more subjects experience a Grade 3 or higher study drug-related AE of anaphylaxis, cytokine release syndrome, or immune complex disease
- If 1 or more subjects experience a serum ALT > 10 x ULN
- If 1 or more subjects experience a serum ALT or AST > 3 × baseline value with a concomitant total bilirubin > 2 × ULN or INR > 1.5
- If 1 or more subjects experience clinical manifestations of hepatic decompensation

If a cohort is stopped, no further study drug will be administered at the dose level and further dose escalation/progression will be suspended. An ad hoc SRC meeting will be held, and only following SRC approval may dosing be resumed at the same or a higher dose level; if required, additional approval from the concerned regulatory authority and the independent ethics committee (IEC)/institutional review board (IRB), in accordance with applicable requirements, will be obtained. De-escalation to a lower dose will be allowed at Sponsor discretion.

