8. STUDY PROCEDURES

The Schedule of Study Assessments is provided in [Appendix 2](#) for Part A and [Appendix 3](#) for Parts B, C, and D. Unscheduled visits are permitted at the discretion of the investigator as needed for safety assessment. Fasting is not required for any study procedure/assessment

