8.13. Clinical Laboratory Assessments

Clinical laboratory tests that will be performed in this study are presented in [Appendix 9](#). In the event of an unexplained clinically relevant abnormal laboratory test occurring after study drug administration, the test may be repeated and followed up at the discretion of the investigator until

it has returned to the normal range or stabilized, and/or a diagnosis is made to adequately explain the abnormality.

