- ^o Includes samples for ADA and neutralizing antibodies (NAb), as applicable. Additional unscheduled samples for immunogenicity analysis may be collected if an immunologic related event is suspected. Immunogenicity sampling beyond the planned follow-up period may occur based on emerging results. Further details can be found in Section 8.16 .
- ^p Local tolerability only needs to be assessed for subjects who are administered study drug by SC injection. On Day 1, local tolerability should be assessed at approximately 1 hour post-dose. At the discretion of the investigator, unscheduled visits are permitted as needed for follow up of any unresolved local tolerability symptoms.
- ^q All AEs related to screening activities must be collected starting at the time of consent; any other events occurring during the screening period should be reported as medical history. All SAEs must be collected from the time of consent onwards. Further details can be found in Section 9.3.

APPENDIX 3. PART B, C, AND D SCHEDULE OF ASSESSMENTS FOR SAD COHORTS IN SUBJECTS WITH CHRONIC HBV INFECTION WITHOUT CIRRHOSIS

Part B, C, and D														
Study Stage	Screening	Dosing Day ^a	Post-dose Follow-up Period							Extended Follow-up Period ^b				
Study Visit Week					W1		W2	W4	W8/ET ^c	W12	W16	W24	W32	W40 / EF ^d
Study Visit Day±Visit Window	D -42 to -1	D1 ^e	D2	D4+1	D8±1	D11±1	D15±2	D29±2	D57±7	D85 ±7	D113 ±7	D169 ±7	D225 ±7	D281 ±7
Informed consent	X													
Demography	X													
Medical history including HBV genotype ^f	X													
Inclusion/exclusion criteria	X	X ^g												
Full physical examination ^h	X			X					X					
Symptom-directed physical examination		X	X		X		X	X						
Body weight	X													
Height	X													
Vital signs ⁱ	X	X	X	X	X		X	X	X					
Safety ECGs ^j	X													
Pregnancy test ^k	X	X						X	X	X	X	X	X	X
FibroScan ^l	X													
Screening viral serology ^m	X													
Liver Function Tests ⁿ	X	X	X	X	X		X	X	X	X	X	X	X	X
Serum Chemistry ⁿ	X	X	X	X	X		X	X	X	X	X	X	X	X

Part B, C, and D														
Study Stage	Screening	Dosing Day ^a	Post-dose Follow-up Period							Extended Follow-up Period ^b				
Study Visit Week					W1		W2	W4	W8/ET ^c	W12	W16	W24	W32	W40 / EF ^d
Study Visit Day±Visit Window	D -42 to -1	D1 ^e	D2	D4+1	D8±1	D11±1	D15±2	D29±2	D57±7	D85 ±7	D113 ±7	D169 ±7	D225 ±7	D281 ±7
Hematology ⁿ	X	X	X	X	X		X	X	X					
Coagulation Parameters ⁿ	X	X	X	X	X		X	X	X					
Complement testing ^{n,o}		X			X		X							

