- ^b Following Week 8, subjects with > 2-fold HBsAg reduction at Week 8 should be followed for up to 40 weeks or until the reduction in HBsAg is < 2-fold relative to baseline at 2 consecutive collections, whichever occurs first. The extended follow-up may be discontinued at the Sponsor's discretion based on emerging data.
- ^c If a subject withdraws participation prematurely from the study prior to the Week 8 visit, Week 8/ET assessments should be performed.
- ^d If a subject withdraws participation prematurely from the study after the Week 8 visit and prior to the Week 40 visit, Week 40/EF assessments should be performed.
- ^e Assessments performed predose unless otherwise specified.
- ^f A complete medical history will be taken at screening. Any changes should be updated prior to dosing. HBV genotype information will also be collected, if available. For subjects with HBV DNA > 500 IU/mL, viral sequencing from the HBV resistance surveillance sample may be used to determine genotype.
- ^g Prior to study drug administration on Day 1, subject eligibility will be confirmed.
- ^h See Section 8.3 for assessments to be performed during a full physical examination.
- ⁱ Vital signs (blood pressure, pulse rate, respiratory rate and temperature [oral preferred]) should be measured after the subject has rested comfortably for approximately 10 minutes. On Day 1, vital signs should be measured within 2 hours prior to dose, at 2 hours post-dose (+/- 1 hour), and at 6 hours post-dose (+/- 1 hour). On all other visit days, vital signs are only required to be recorded once during the visit.
- ^j ECGs should be measured in the supine position after the subject has rested comfortably for approximately 10 minutes.
- ^k WOCBP are required to have pregnancy tests. A blood pregnancy test will be performed at screening and a urine pregnancy test will be performed thereafter. Negative pregnancy test must be confirmed prior to study drug administration.
- ^l Does not need to be performed if the subject has had a FibroScan in the 6 months prior to screening or liver biopsy in the year prior to screening that confirmed the absence of Metavir F3 fibrosis or F4 cirrhosis.
- ^m See Section 8.10 for viral serology parameters.
- ⁿ Clinical laboratory and urinalysis parameters are described in Appendix 9.
- ^o Additional samples may be collected at any time post-dosing if immune-complex disease is suspected.
- ^p Drugs of abuse included in the screen are described in Section 8.14.

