APPENDIX 7. DOSING SCHEDULE

VIR-3434-1002 Cohort
Dosing Schedule

*The Part B optional cohorts may be dosed at a lower, equivalent, or intermediate dose level relative to the dose levels explored in the planned Part B cohorts, or after cohort 5b at a dose level not exceeding 900 mg.

** Parts C and D may be enrolled after SRC review of available data for all subjects in Part A and Part B through the Week 4 visit for the cohort of subjects in Part B who received a matching or higher dose relative to the proposed starting dose level in Part C and/or D.

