Part B, C, and D: • Urinalysis	Day 1 (Baseline) Week 1 Week 2	1 8 15	≤1 Pre-dose [1, 11] (11, min(≥64, Ext FU Day 1)]
Part B, C, and D: • Local tolerability	Day 1 (Baseline) Day 2 Day 4 Week 1	1 2 4 8	≤1 Pre-dose [1, 3] (3, 6] (6, min(≥64, Ext FU Day 1)]
Part B, C, and D: • Physical examination	Screening (Baseline) Day 4 Week 8	<1 4 57	<1 Pre-dose [1, 30] (30, min(≥64, Ext FU Day 1)]
CCI			
Extended Follow-Up Period (Part B, C, and D)			
• Pregnancy test • Liver function test • Serum chemistry • Immunogenicity • HBsAg and Anti-HBS • HBV DNA (Part D)	Ext Week 12 Ext Week 16 Ext Week 24 Ext Week 32 Ext Week 40	85 113 169 225 281	(Ext FU Day 1, 99] (99, 141] (141, 197] (197, 253] (253, ≥288]

Table 7-1 Analysis Visit Windows for Safety and Antiviral Assessments			
Assessment	Analysis Visit¹	Target Study Day	Analysis Visit Window (in study days)^{2, 3, 4, 5}
Part B, C, and D: 
 • HBV RNA • HBcrAg 	Ext Week 12 Ext Week 24 Ext Week 32 Ext Week 40	85 169 225 281	(Ext FU Day 1, 113] (113, 197] (197, 253] (253, ≥288]
CCI			
Part B, C, and D: 
 • HBeAg and Anti-HBe 	Ext Week 40	281	(Ext FU Day 1, ≥288]

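### INR is neither scheduled nor required by reflex at some visits where liver tests are drawn, so the INR limb of the open-ended liver stopping rule rests there on a discretionary test

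*Protocol*

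**What the plan says.** Protocol Section 5.6.1 lists the cohort stopping criteria for all Parts. One of them is met by a single subject with ALT or AST above 3 × baseline and "concomitant total bilirubin > 2 × ULN or INR > 1.5". No criterion has a last day or week. If a cohort is stopped, dosing at that level ends and further progression is suspended until the SRC approves.

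Appendix 9 places INR under coagulation. ALT, AST and bilirubin are in the liver panel. Both schedules list "Coagulation Parameters" as a separate row, with fewer marked visits than the liver row.

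Under Appendix 3, footnote b, "subjects with > 2-fold HBsAg reduction at Week 8 should be followed for up to 40 weeks", unless the reduction falls below 2-fold at two consecutive collections or the Sponsor ends follow-up. Liver tests continue in that period and coagulation does not. The readable rows of SAP Appendix 2, Table 7-1, under "Extended Follow-Up Period (Part B, C, and D"), agree: they list liver tests and chemistry, not coagulation.

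Two provisions tie further tests to an enzyme rise. Appendix 9, footnote a, requires creatine kinase when ALT or AST exceeds 2 × the Day 1 value. Appendix 3, footnote u, allows extra HBV DNA and resistance samples when ALT more than doubles. Neither mentions INR. Other testing is optional: "Unscheduled visits are permitted at the discretion of the investigator as needed for safety assessment" (Section 8), and for an unexplained abnormal result "the test may be repeated and followed up at the discretion of the investigator" (Section 8.13).

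**The concern.** A stopping rule with numeric limits should be assessable whenever its first condition can be met. Here the enzyme half can be met at any scheduled liver panel, but at some of those visits the INR half can be assessed only if someone chooses to order the test. Two subjects with identical findings could then lead to different decisions about dosing.

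Hepatotoxicity is a named risk for subjects with HBV (Section 2.4), and liver tests in extended follow-up run to Week 40. A late result can still bear on dosing. Appendix 7 says "Parts C and D may be enrolled after SRC review of available data for all subjects in Part A and Part B" through Week 4 of the relevant Part B cohort, so Weeks 12 to 40 of Part B may overlap dosing in Parts C and D. In Part A, Day 15 is the Week 2 visit that closes the SRC's escalation window, and it has liver tests without INR.

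**Working it through.** The plan states no figure to reproduce. The check is a count of marked visits, followed by the region that only the INR limb can catch.

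**Inputs.** Visit grids: Protocol Appendices 2 and 3. Panel contents: Appendix 9. Limits: Section 5.6.1. Screening limits: Sections 6.3 and 6.5.

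**Count of scheduled post-dose panels**

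| Part and period | Liver tests | Coagulation (INR) | Liver panels without INR |
|---|---|---|---|
| A, to Week 24 | D2, D4, D8, D15, D29, D57, D85, D127, D169 = 9 | D8, D29, D57, D85, D169 = 5 | D2, D4, D15, D127 = 4 of 9 |
| B, C, D, to Week 8 | D2, D4, D8, D15, D29, D57 = 6 | the same 6 | 0 of 6 |
| B, C, D, extended | W12, W16, W24, W32, W40 = up to 5 | 0 | all, up to 5 of 5 |

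For a subject who completes extended follow-up, the span after the last scheduled INR is Day 281 − Day 57 = 224 days, or 32 weeks.

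**Reflex check.** Some Appendix 3 footnotes are redacted. The coagulation row carries only footnote n, which is readable and simply points to Appendix 9. The missing text therefore does not explain the absence of INR from that row.

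**What only INR can catch.** With bilirubin ≤ 2 × ULN, the paired rule needs INR > 1.5. A separate rule already stops on ALT > 10 × ULN. The ALT range left to INR is therefore above 3 × baseline and up to 10 × ULN. I assume Day 1 ALT lies within the screening limit.

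- Baseline 1 × ULN (the Part A limit): 3 × 1 = 3, so > 3 to 10 × ULN.
- Baseline 2 × ULN (the Part B and C limit): 3 × 2 = 6, so > 6 to 10 × ULN.
- The range is empty once 3 × baseline ≥ 10 × ULN, that is baseline ≥ 10/3 = 3.33 × ULN. Only Part D, with a limit of 5 × ULN, allows this.
- At an assumed low baseline of 0.4 × ULN: 3 × 0.4 = 1.2, so > 1.2 to 10 × ULN. The lower end is a Grade 1 value in SAP Appendix 5.

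AST has no 10 × ULN rule, so a rise in AST alone has no such ceiling. Entry excludes INR above ULN in every Part, so an INR above 1.5 would normally be a new change.

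**The case against.** The case for leaving the schedule alone is substantial. Section 5.6.1 is applied as determined by the Sponsor, who is unblinded. Its first criterion lets the sponsor or investigator suspend dosing for a related finding until it is better understood, which could cover the wait for an INR. Albumin, another marker of liver synthetic function, is in the chemistry panel at every one of these visits. After Week 8, Parts B, C and D still collect all SAEs and targeted new-onset hepatic disorders (Section 9.3).

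The reduction after Week 8 also looks deliberate: hematology, vital signs and physical examinations end with coagulation. Section 2.4 sets the 4-week SRC review to cover the expected timing of hepatotoxicity, and INR in Parts B, C and D runs to twice that. The SRC also looks again later: "The SRC will undertake safety data review prior to initiation of dosing a new cohort in the study". Its charter, which is not among the documents, may address INR.

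Most of this stands, and it makes the gap small. It does not supply the missing value. The first criterion rests on opinion, albumin is not an input to the rule, and the SRC can see an enzyme rise but not an INR that was never drawn. Under Sections 9.1.1 and 9.1.3, a laboratory abnormality without symptoms or need for intervention is not recorded as an adverse event, so event-based criteria may not respond.

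A reader might infer that the liver rule stops working after Week 8, or that liver injury would go unseen. The documents do not support that: scheduled ALT, AST and bilirubin continue to feed the bilirubin limb, and ALT also feeds the > 10 × ULN rule. Nor can the number of affected subjects be read from the dose modelling in Section 2.3.2. The predicted 0.3 log10 decline at 6 mg is a mean with no stated time point and an assumed baseline of 50 IU/mL, so it does not show who passes an individual 2-fold threshold at Week 8.

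**Conclusion.** The mismatch between rule and schedule is real and narrow. INR accompanies 0 of up to 5 extended follow-up panels in Parts B, C and D and is absent from 4 of 9 post-dose panels in Part A. Through Week 8 in Parts B, C and D the pairing is complete, so subjects there who do not enter extended follow-up are unaffected at scheduled visits.

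A missed trigger needs several things together: ALT or AST above 3 × baseline, ALT no higher than 10 × ULN, bilirubin no higher than 2 × ULN, INR above 1.5, no INR ordered, no other criterion met, and, because dosing is single, someone still to be dosed. The documents give no rate for this combination and no enrolment pace, so neither the number of events nor the number of later cohorts affected is estimated. The count rests on the grids as printed; the ALT ranges rest on Day 1 values within the screening limits. This is a low-cost improvement, not a flaw that undermines the safety plan.

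**What to change.** Add a footnote to Appendices 2, 3 and 9, modelled on the creatine kinase footnote. Whenever ALT or AST exceeds 3 × the Day 1 baseline at a visit without scheduled coagulation, INR is required. It should be run on the same draw where possible, otherwise on a prompt repeat draw with ALT, AST and bilirubin. State that this paired result counts as concomitant for Section 5.6.1.

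To avoid tests for trivial rises from a low baseline, the sponsor may add an absolute floor for ALT or AST. Section 5.6.1 must then carry the same floor, or rule and test will disagree again. If the INR limb is meant to end at Week 8 in Parts B, C and D, Section 5.6.1 should say so; that would not settle the Part A visits.

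The cost is one footnote and an occasional extra coagulation sample, possibly with a return visit. How many subjects would need one cannot be estimated from the documents. No routine sampling is added.

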5.3. Study Drug Dosing, Study Progression, and Dose Escalation

Progression rules for cohorts are based on the absence of substantial safety signals. Standard toxicity grading according to the current Common Terminology Criteria for Adverse Events (CTCAE v 5.0) will be used to grade AEs. The decision to permit enrollment of an optional cohort will be made by the SRC based on a review of available safety, tolerability, and antiviral activity data (Parts B, C, and D only).

For cohorts in which a maximum dose level has been provided in lieu of an exact dose level, a final dose will be proposed by the Sponsor based on available safety and efficacy data (Parts B, C, and D only), prior to enrollment of the cohort. This dose level must be reviewed and approved by the SRC prior to enrollment of the cohort.

The maximum dose escalation factor in Study Parts A and B will not exceed 5-fold.

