5.3.3. Part C Study Drug Dosing, Study Progression, and Dose Escalation

Overview: Part C is optional and may be conducted if VIR-3434 is found to have an acceptable safety and tolerability profile in HBeAg-negative subjects with HBsAg levels < 3,000 IU/mL in Part B. For cohorts in Part C, HBeAg-negative and HBeAg-positive subjects with HBsAg \geq 3,000 IU/mL will be enrolled.

There are 3 optional cohorts in Part C each evaluating up to 900 mg SC (Table 5). Cohort 1c will be the first cohort to initiate enrollment. Doses explored in Part C cohorts will not exceed the highest dose level in Part B that was determined to be safe by the SRC. Part C cohorts may be enrolled in parallel.

Initiation of Part C: Cohort 1c may be initiated after SRC review of available data for all subjects in Part A and Part B through the Week 4 visit for the cohort of subjects in Part B who are receiving a matching or higher dose.

Table 5: Part C Cohort Overview

Study Part	Cohort	Route	Dose Level	Active:Placebo
C	1c (optional)	SC	up to 900 mg	6:2
C	2c (optional)	SC	up to 900 mg	6:2
C	3c (optional)	SC	up to 900 mg	6:2

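### After a cohort stop, Protocol 5.6.1 does not require open lower-dose Part C or D cohorts to pause for the ad hoc SRC meeting, and its de-escalation sentence conflicts with 5.2 and 5.3

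*Protocol*

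**What the plan says.** Protocol 5.6.1 gives the effect of a stop as follows: "no further study drug will be administered at the dose level and further dose escalation/progression will be suspended". The SRC must then meet ad hoc, with no time limit given. The condition for restarting is this: "only following SRC approval may dosing be resumed at the same or a higher dose level". The paragraph ends: "De-escalation to a lower dose will be allowed at Sponsor discretion".

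Other sections give the SRC control when a cohort opens:

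- 5.2: "The SRC will undertake safety data review prior to initiation of dosing a new cohort in the study in accordance with the SRC Charter".
- 5.3, optional cohorts (all of Parts C and D): "The decision to permit enrollment of an optional cohort will be made by the SRC".
- 5.3, cohorts given only a dose ceiling: "This dose level must be reviewed and approved by the SRC prior to enrollment of the cohort".

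Sections 5.3.3 and 5.3.4 allow Part C and Part D cohorts to enroll in parallel. Of Part C, 5.3.3 adds: "Cohort 1c will be the first cohort to initiate enrollment". Section 5.3.4 says the same of 1d.

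**The concern.** A stop in Part C or D may be the first serious signal in that population. Part C enrolls subjects with HBsAg of at least 3,000 IU/mL. Part D enrolls subjects off NRTI with HBV DNA of at least 1,000 IU/mL and allows ALT or AST up to 5 x ULN, against 2 x ULN in Parts B and C (6.4, 6.5). Section 2.4 presents the Part B limit of HBsAg below 3,000 IU/mL as protection against immune complex disease and hepatotoxicity. A lower dose in Part C or D is therefore not clearly a safe dose.

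An open cohort's cleared sentinels give limited reassurance. They are watched for at least 72 hours (5.1.3, 5.1.4), while 2.4 bases the SRC's escalation review on up to 4 weeks of data because of when these toxicities are expected. After hepatic decompensation at 300 mg in Part C, for example, further Part C subjects could be dosed at 75 mg before the SRC had considered the event.

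The rule also sits oddly beside 5.5. Replacing a subject who left because of an AE that does not meet a stopping criterion needs SRC confirmation. De-escalated dosing after an event that does meet one is left by 5.6.1 to the Sponsor.

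**Working it through.** The plan gives no figure to reproduce, so the check compares texts and then counts subjects.

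**Step 1: what a stop halts.** It halts dosing at that dose level and suspends further escalation or progression. 'Progression' is not defined. Section 5.3 applies it to cohorts ("Progression rules for cohorts are based on the absence of substantial safety signals"), which suggests moving from one cohort to the next. If it meant all dosing, the restriction to the dose level would be redundant. Nothing else in the paragraph names an open cohort at a lower dose.

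**Step 2: whether another SRC control reaches an open lower-dose cohort.** The controls in 5.2 and 5.3 act before a cohort is enrolled or dosed. An open cohort has already passed them, on data that predate the event. Cohorts 1c and 1d open on Week 4 data from a Part B cohort at a matching or higher dose, and parallel enrollment means later cohorts need not wait for data from earlier ones in the same Part. In Parts A and B a parallel cohort must be at or below a dose already found acceptable in that Part, so this limb is confined to Parts C and D.

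**Step 3: de-escalation.** There are 5 + 7 + 3 + 3 = 18 cohorts. Three have fixed doses (1a, 1b, 2b), so 18 - 3 = 15 fall under the dose-approval rule in 5.3. All 3 + 3 = 6 cohorts in Parts C and D are optional, so the SRC decides whether each opens. De-escalation through a new cohort is therefore under SRC control. The unsettled case is the undosed remainder of a stopped cohort: 5.6.1 says Sponsor discretion, while 5.3 ties SRC approval to the specific dose.

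**Step 4: how many subjects.** Each cohort has 8 subjects: 2 sentinels (1:1), then 6 subjects (5:1). The counts assume that both sentinels have been dosed and ignore replacements. Doses are from SAP Table 2.

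| Situation | Undosed subjects | Of these, active |
|---|---|---|
| Stopped cohort, all dosed | 8 - 8 = 0 | 0 |
| Stopped cohort, sentinel triggers the stop | 8 - 2 = 6 | 5 |
| Stop at 3c (300 mg); 1c (18 mg) and 2c (75 mg) fully dosed | 0 | 0 |
| Stop at 3c; 1c fully dosed, 2c sentinels only | 6 | 5 |
| Stop at 3c; 1c and 2c sentinels only | 2 x 6 = 12 | 2 x 5 = 10 |
| Stop at 2d (300 mg); 1d (75 mg) fully dosed | 0 | 0 |
| Stop at 2d; 1d sentinels only | 6 | 5 |

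The 12 after a stop at 3c and the 6 after a stop at 2d are theoretical maxima. They are unlikely because 1c and 1d open first. Neither document reports how far cohorts overlapped.

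**The case against.** The strongest reply is that 5.3 already governs de-escalation. SRC approval attaches to a specific dose, so a cohort approved at 300 mg has no approval for 75 mg, and changing a fixed dose would need a protocol change. On that view, Sponsor discretion means only that the Sponsor may choose to de-escalate, with 5.2 and 5.3 still applying. This largely stands. A reader might infer that de-escalation bypasses the SRC altogether; the documents do not support that. They support an unreconciled conflict, in which 5.6.1 names the SRC for the same or a higher dose and then, by contrast, names only the Sponsor for a lower one.

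On the open cohorts, the section headings under 5.3 speak of study progression, which may be wider than movement between cohorts. The text does not settle this, but the wide reading leaves the dose-level restriction with nothing to do.

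Parts C and D also have a dose cap, the highest Part B dose judged safe. That cap comes from a different population. In Parts A and B too, earlier acceptance would predate a new event, but there it concerns the same Part's population.

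Other safeguards are real. The Sponsor is unblinded, the first stopping criterion lets the Sponsor or investigator call for suspension of further dosing, and 11.2.1 lets the Sponsor terminate any cohort. All of these are discretionary. The SRC Charter, which sets the SRC's data review requirements, is not among the documents and may require the pause.

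**Conclusion.** The point holds as a gap for open lower-dose Part C and D cohorts and as a conflict over de-escalation. After a stop, 5.6.1 does not make those cohorts wait for the mandatory ad hoc meeting, and no other section reviewed here does so. This rests on reading 'progression' as movement between cohorts and on the Charter being silent.

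The size is not established: 0 to 6 undosed subjects in a stopped cohort, and for open cohorts a number that depends on unknown overlap. A reader might take the theoretical 12 after a stop at 3c as an expected exposure, or infer that subjects were in fact dosed in this way. Nothing in the documents shows that a stop occurred or that cohorts overlapped to that extent.

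This is a cheap improvement in subject protection, of lower priority. The SAP lists 1c to 3c and 1d to 2d as enrolled and 3d as not enrolled, so its practical value depends on whether dosing remains.

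**What to change.** Replace the last sentence of 5.6.1 with:

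> De-escalation to a lower dose may be proposed by the Sponsor and requires SRC approval. In Parts C and D, dosing in any open lower-dose cohort of the same Part will pause until the ad hoc SRC has reviewed the event and agreed that dosing may continue.

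This brings 5.6.1 into line with 5.2 and 5.3 and uses a meeting that is already required. It does not pause Part D after a Part C event, or the reverse; that stays a matter of judgment.

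The cost is a short pause in open cohorts. Of the 8 stopping criteria, 5 require a relationship to study drug and 8 - 5 = 3 do not (ALT above 10 x ULN; ALT or AST above 3 x baseline with raised bilirubin or INR; hepatic decompensation). The pause would therefore sometimes follow an unrelated event or one on placebo. The change also needs a protocol amendment with IRB or IEC approval (11.1.10). If the Charter already contains the rule, a cross-reference in 5.6.1 would do for the pause, but the de-escalation sentence should still be corrected.
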